participants will also provide a urine sample which will be tested for drugs and pregnancy (if applicable) to ensure participants are positive for THC. Participants are trained on the driving simulator computer tasks. If participants are determined to be eligible, they will be scheduled for the following two visits. In a double-blind, placebo-controlled, random order cross-over study of single dose THC (dronabinol) at physician determined doses of 10-80mg, participants will receive THC capsules or identical placebo on two separate study visits, randomized for order. The MGH research pharmacy will generate a blinded randomization code for order of dosing and will dispense blinded drug in the dose ordered and identical placebo for use on separate study days. In order for a complete washout of effects, and to minimize the effect of repeat testing for the neuropsychology tasks, study visits must be at least 1 week apart. On each study day, participants will have a light standardized breakfast after overnight fast and sleep. They will be asked not to deviate from normal behaviors (e.g. if they drink caffeinated beverages or smoke cigarettes in the mornings, they will be asked to do so on the study day so that no symptoms of caffeine or nicotine withdrawal will appear during the scanning period. On each study day, participants will undergo baseline fNIRS testing (see above “Cognitive Tasks during FNIRS testing”), substance use history interview (timeline follow back), two sets of baseline vital signs, a driving simulator computer task refresher, and several questionnaires (HADS, URGE, PSQI, CWS). Dronabinol or placebo will be administered once morning procedures are complete, after which point heart rate, blood pressure, and responses to DEQ and BAES questionnaires will be monitored at 20 minute intervals. The second fNIRS session will be conducted at approximately 90 minutes post dose, followed by driving simulator computer tasks. A field test of sobriety will be conducted immediately following the second fNIRS assessment. The third fNIRS session will be conducted at approximately 220 minutes post dose, prior to participant discharge. See Below for schematic:

Subjects who participated in Phase 1 will be eligible for Phase 2, but enrollment in Phase 1 is not a requirement for Phase 2. Therefore, new subjects who have not completed Phase 1 will also be eligible for Phase 2.

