dose of dronabinol (20 mg, 35 mg, 50 mg). In this single-blinded phase, the subject will not know which dose he/she is receiving. The protocol for the study visit will be identical. As there are three levels of drug exposures, there are 6 possible orders in which subjects can receive the three doses (e.g. high, medium, low; medium, low, high; etc). Subjects will be randomly assigned to one of the 6 possible orders according to a randomization schedule generated by the study staff using a random number generator and computer program. In order for a complete washout of effects, and to minimize the effect of repeat testing for the neuropsychology tasks, study visits must be at least 1 week apart. See below for schematic:

Subjects who participated in Phase 1 or 2 will be eligible for Phase 3, but enrollment in Phase 1 or 2 is not a requirement for Phase 3. Therefore, new subjects who have not completed Phase 1 or 2 will also be eligible for Phase 3.

Driving Simulation: During this phase, we will use a computer-programmed driving simulator to assess motor coordination of the participants. The simulation will be programmed in STISIM on the computer and will be administered by a trained research coordinator. Subjects will be trained on this task during the screening task during the screening visit and given a refresher training on the task before testing. The task is performed on a laptop with the use of the keyboard, a joystick, and a foot pedal. Participants perform tasks where they must center an object on the screen using the joystick, in addition to identifying numbers with the tap of the foot pedal.

Participants: 60 healthy, weekly or greater MJ users, aged 18-55, will be enrolled. Participants must test positive for cannabis, and negative for other addictive drugs and have no serious unstable medical illness to participate in the Phase III (See Participant Selection Section).

Biostatistical Analysis

Data variables collected for study

Standardized questionnaires, assessing drug use, personality characteristics, and anxiety will be collected, as well as task data and neural signaling data from the fNIRS testing sessions.

All data will be collected and managed using REDCap electronic data capture tools (Harris 2009) hosted with Partners HealthCare.

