For each stimulation run, each smoothed oxy-/deoxy-hemoglobin time series will be examined for periodic amplitude fluctuations. Expected fluctuations include heart rate (~1Hz), breathing and/or “v-waves” (~0.1Hz), as well as any fluctuations induced by the experimental paradigm. If the former sources of noise are substantial, an attempt will be made to filter out these fluctuations (in Fourier space). Any analysis of filtered data will be compared to an analysis of the corresponding non-filtered data. The oxy-hemoglobin portion of the experimentally induced changes are expected to be 4-9 sec out of phase with the paradigm onsets and offsets (as seen in fMRI work as well as in prior optical recordings).

Study endpoints

As this is not a clinical trial, we will collect data from up to 20 participants in Phase 0, up to 100 participants in Phase I, up to 200 in Phase II and up to 60 in Phase III in order to investigate whether we can determine the brain signals involved in marijuana intoxication. Given that the planned studies are pilot in nature, and that we will be using

a recently developed instrument, the relevant effect sizes are unknown and therefore power analysis cannot be adequately performed. However, some estimates can be made. The biological basis for the signals measured by the optical technique is the same as the basis for fMRI and PET scanning. In a similar study using PET (*R.J. Mathew et al. / Psychiatry Research: Neuroimaging 116 (2002) 173–185*), indices of rCBF, intoxication and physiology were measured at baseline and 30, 60, 90 and 120 min. after an intravenous infusion of 0.15 or 0.25 mg of THC, or placebo. Significant increases were seen in global perfusion and in the frontal, insular and anterior cingulate regions. This study had a sample size of 47 subjects in each group. Therefore, we will collect data in 100 participants, as this is a conservative estimate of the power we will need to detect an effect.

Statistical methods

Statistical analysis of data will be performed using SPSS, STATA, and fNIRS analysis software.

Risks and Discomforts

Potential adverse events due to dronabinol:

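### Phase 3 masks only the participant and uses a staff-made order schedule; extending the pharmacy masking already used in Phase 2A would reduce, though not remove, staff influence on the dose comparison

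*Protocol*

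**What the plan says.** **Phase 3 (protocol, section X, Phase 3).** Participants attend three sessions and receive 20, 35 or 50 mg, one dose per session. The protocol notes that "there are 6 possible orders in which subjects can receive the three doses" and assigns each participant to one of them by a "randomization schedule generated by the study staff using a random number generator and computer program". On masking it says: "In this single-blinded phase, the subject will not know which dose he/she is receiving". Other procedures are those of Phase 1, with a driving simulator run by a research coordinator. The enrolment statement is "60 healthy, weekly or greater MJ users, aged 18-55, will be enrolled".

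**Phases 2A and 2B (same section).** Phase 2A is double-blind, and the protocol states how: "The MGH research pharmacy will generate a blinded randomization code for order of dosing and will dispense blinded drug", with identical placebo. Phase 2B is also double-blind and refers back to Phase 2A for dronabinol administration.

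**Steps that involve judgement.** Under Phase 1 procedures, a third scan is optional and a further late scan may follow if the results suggest continued intoxication. Under fNIRS Data Analysis, if physiological noise is substantial, "an attempt will be made to filter out these fluctuations". The next sentence commits to comparing filtered with unfiltered analyses.

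**SAP.** Study Design covers Phases 2A and 2B only.

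**The concern.** Phase 3 has no placebo session, so its only randomised contrast is dose against dose. Staff who know the dose at a visit, and expect a gradient, are in a position to affect that contrast. The protocol gives no reason for masking this phase less fully than the two before it.

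The mechanism is also less developed. Phase 3 inherits Phase 1 procedures, which describe no masking, so the pharmacy arrangement does not carry over by reference. Nothing says that the three doses are dispensed in matched form. The SAP contains no Phase 3 analysis, so no prespecified rule limits the later choices about signal processing. At stake is the reading of Aim 2: at which doses an effect on task performance or prefrontal activity is seen.

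**Working it through.** The protocol states no power or effect-size figure for Phase 3, so the check is mainly a comparison of text.

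**1. The design arithmetic is sound.** Three doses give 3! = 6 orders. With 60 participants, a balanced schedule has 60/6 = 10 per order and 60 x 3 = 180 dosing visits. Both are ceilings, because Study endpoints says up to 60.

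**2. Masking by phase.**

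| | Phase 2A | Phase 2B | Phase 3 |
|---|---|---|---|
| Stated level | double-blind | double-blind | single-blind (participant) |
| Source of order | research pharmacy | random assignment to 1 of 4 sequences; dronabinol administered as in 2A | study staff |
| Matching of product | identical placebo | as 2A for dronabinol | not stated |
| Separation of roles | code held as blinded | unmasked staff named for ethanol preparation at one site | not stated |

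**3. Where knowledge of dose could act in Phase 3.**
- *Simulator refresher and session conduct.* The refresher comes before testing. Its timing relative to dosing is not given for this phase.
- *Late scans.* The third scan depends on available time, and the 330-minute repeat depends on a judgement of continued intoxication. Neither can change the second scan, which is set at about 100 minutes.
- *Noise filtering.* Whether noise is substantial is a judgement. The comparison with unfiltered data makes the choice visible but does not mask the person making it.

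**4. Where it has little room to act.** N-back responses are collected by software, questionnaires are completed by participants on laptops, fNIRS is instrument-recorded and the simulator is computer-programmed. The field sobriety test is described only for Phases 2A and 2B.

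**5. Illustration only.** The documents give no size for any staff effect, so the shifts below are assumptions. With no true dose difference, a two-sided 5% test and a systematic shift of m standard errors, the rejection rate is Φ(m − 1.96) + Φ(−m − 1.96).
- *Shift in SDs of a single measurement, visits uncorrelated:* SE = √(2/60) = 0.183. Shifts of 0.1 and 0.2 SD give m = 0.55 and 1.10, and rejection rates of about 8.5% and 20%.
- *Shift in SDs of the paired difference:* m = b√60. For b = 0.05, 0.1 and 0.2 the rates are 6.7%, 12.1% and 34.1%. With 48 completers (an assumed 20% loss) they are 6.4%, 10.7% and 28.3%.

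The two scales agree when the within-person correlation is 0.5, since √(2 × (1 − 0.5)/60) = √(1/60). The result depends heavily on the assumed shift and the scale, so it shows sensitivity and does not estimate the bias.

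**The case against.** The case against acting is substantial. Phase 3 is openly declared single-blind, in studies that the protocol calls pilot in nature. Its outcomes are mostly automated or self-reported. The stated triggers for late scans are time and scan results, not dose. N-back familiarisation comes before dosing. Orders come from a random number generator and every participant is scheduled for all three doses, so a known schedule cannot create the usual imbalance in participant characteristics between doses. All of this stands, and it limits the point to visit-level conduct and data handling.

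A reader might also infer more than the documents support:
- *That the same people make the schedule, run the sessions and process the data.* The protocol says only that study staff generate the schedule. What is missing is a stated separation of roles.
- *That participant masking fails.* The protocol states that the participant will not know the dose. Silence on capsule matching is a missing operational detail and does not show failure.
- *That full masking would remove the bias.* Risks and Discomforts says that effects on mood, cognition and perception appear dose-related, so visible intoxication could still hint at the dose.
- *That the false-positive rate is inflated by a known amount.* No document supports any particular shift.

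The objection does not supply a reason for leaving session staff and data processors unmasked when a blinded pharmacy route already exists in the same protocol.

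**Conclusion.** The point holds as a low-cost improvement to one phase. Phase 3 masks only the participant, uses a schedule made by study staff and describes no separation of roles, while Phase 2A, and Phase 2B by reference for dronabinol, use blinded pharmacy supply. Up to 180 dosing visits are exposed through a few discretionary steps. Whether any bias would arise, and how large it would be, cannot be determined from the documents.

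The consequence is confined to Aim 2. The SAP's two primary outcomes and six p-values use no Phase 3 data, so a reader should not take this as a threat to the primary results. The conclusion assumes that Phase 3 visits, or at least Phase 3 data processing, remain to be done. The documents do not say.

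**What to change.** For Phase 3 visits not yet run:
- have the research pharmacy generate and hold the six-order schedule;
- dispense the three doses already in the protocol in capsules matched in number and appearance;
- keep session staff and fNIRS data processors masked to dose, and say so in the protocol;
- keep a code-break at the pharmacy for safety.

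At minimum, require fNIRS processing, including the filtering decision, to be done on files that do not show the dose. This is possible even after data collection. If single-blinding is kept, the protocol should give the reason.

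The cost is a protocol amendment and extra pharmacy dispensing. The charge is probably modest because the trial already uses the service, but that is a judgement: the documents give no cost. No added visits or participants are needed.

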MGH Center for Addiction Medicine study staff will conduct telephone screening of approximately 2000 potential subjects. A telephone screening will distinguish the majority of likely eligible subjects from those not likely to meet eligibility criteria. This will consist of a brief discussion of the research study, confirming a potential participant's interest in participation and whether he/she meets eligibility criteria and includes asking about cannabis use, current medications, sex, age, pregnancy status, and psychiatric/medical conditions. Screening takes place over the phone in response to a potential participant inquiry (see attached screening telephone script). Those who are not eligible for the experiment based on the phone screen will be informed that they do not qualify for entry into this particular study. The research study consent form will be made available to the participants on their study visit before any study procedures occur. Participants who give permission to receive text messages from the study staff will receive appointment reminders via text through Apptoto three, two, and 1 day(s) before upcoming appointments.

A non-identifying prescreening log will be kept for all individuals screened. The screening log will include a non-identifying subject ID, the date of screening, whether eligibility criteria were met, and enrollment decision or status.

VII. INFORMED CONSENT

Participants who are deemed potentially eligible on the basis of the phone screen will be asked to come in for a study visit. At the time of such visit, informed consent will be obtained by a licensed physician investigator or non-physician investigator with physician back-up prior to administering any study procedures. All participants will be given the opportunity to ask questions to a physician Investigator ([name], or another study physician), and this will be recorded in research records. Contact information of key study staff will be provided and participants will be informed that the co-investigators are available to answer any questions or concerns they may have about the study. All eligible participants will be provided with a copy of their signed consent form.

VIII. PARTICIPANT WITHDRAWAL

Participation is voluntary, and participants may stop being in the study at any time or decide not to join the study. If a participant decides not to participate, they will not be penalized in any way, and will not lose any benefits to which they are otherwise entitled.

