Ethanol dose and administration: We will obtain a breath alcohol concentration (BrAC) of approximately 0.05 BrAC (equal to 1-2 standard drinks). In order to obtain this precise BrAC, we will use established methods of dosing based on previously published procedures (e.g. King 2005, Alcohol Clin Exp Res, Vol 29, No 4, 2005: pp 547–552).

The required volume of 95% ethanol will be calculated from the nomogram published by Watson (1989), and diluted to a final concentration of 20% by volume with diet soda. The nomogram is based on total body water, estimated for each subject using standard equations based on gender, age, height, and weight (Watson et al., 1980). Doses will be prepared at the TCRC by a licensed nutritionist or at CAM by unblinded study staff. He/she will determine the dose according to our spreadsheet for dosing (attached).

In an attempt to standardize the drinking time to 8 minutes, the total dose will be split into 4 equal aliquots and placed in cups with lids. The subject will be given a cup every 2 minutes with instructions to sip the drink using a straw.

- Placebo Ethanol drink will be made as an equal volume of diet soda placed in identical cups with lids and straws. 0.25 ml of 95% ethanol should be floated on the top of the soda in each cup in an attempt to blind the participant.

The alcohol administration procedure will take place approximately 45 min before the start of the second fNIRS session. Before being administered alcohol, study staff will measure breath alcohol levels. Additionally, a study physician/nurse will assess subjects at each study visit prior to any study drug administration for signs of intoxication. Subjects will be terminated from the study if BrAC > 0 or if they exhibit clinical signs of intoxication at time of arrival for study visit.

During this phase, breathalyzer measurements will be taken approximately every 20 minutes after the alcohol administration procedure, until BrACs have returned to <0.01. Participants will be required to stay in the laboratory until BrACs have returned to <0.01. A member of our study staff will then (1) arrange cab service that has an approved partnership with MGH, and (2) escort the participant to the cab at the end of the study visit. Alternatively, it would be acceptable for participants to arrange travel home with a family member or friend. If they choose to do this, a study staff member will ensure that someone is there to bring them home prior to departure.

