Risks: Dronabinol-induced sympathomimetic activity may result in tachycardia and/or conjunctival injection. Its effects on blood pressure are inconsistent, but occasional subjects have experienced orthostatic hypotension and/or syncope upon abrupt standing. Dronabinol also demonstrates reversible effects on appetite, mood, cognition, memory, and perception. These phenomena appear to be dose-related, increasing in frequency with higher dosages, and subject to inter-patient variability.

After oral administration, dronabinol has an onset of action of approximately 0.5 to 1 hours and peak effect at 2 to 4 hours. Duration of action for psychoactive effects is 4 to 6 hours.

Tachyphylaxis and tolerance develop to some of the pharmacologic effects of dronabinol and other cannabinoids with chronic use, suggesting an indirect effect on sympathetic neurons. In a study of the pharmacodynamics of chronic dronabinol exposure, healthy male volunteers (N = 12) received 210 mg/day dronabinol, administered orally in divided doses, for 16 days. An initial tachycardia induced by dronabinol was replaced successively by normal sinus rhythm and then bradycardia. A decrease in supine blood pressure, made worse by standing, was also observed initially. These volunteers developed tolerance to the cardiovascular and subjective adverse CNS effects of dronabinol within 12 days of treatment initiation.

In the clinical trials, the majority of patients were treated with 5 mg/day MARINOL Capsules, although the dosages ranged from 2.5 to 20 mg/day.

Minimization: If there are any concerns about a subject in need of clinical attention, the PI will be made aware of the issue immediately and will consult with appropriate medical personnel (co-investigator: A. [name], or another study physician) to determine appropriate steps. The PI and medically trained co-investigators will assess the needs of the subject and offer the subject either prompt treatment or medical referral, whichever is appropriate for the situation. There is a licensed physician/registered nurse on site 40 hours per week, and other MGH resources can be used as necessary.

Potential adverse events due to ethanol:

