safety limits to avoid the risk of thermal damages. No cumulative harmful effects of such light exposure to the forehead are known, and fNIRS measurements are commonly applied repeatedly or in a continuous manner for monitoring purposes.

Minimization: Subjects who may become uncomfortable during the fNIRS procedure will be able to converse with the experimenter and will be able to communicate any desire or need to stop the procedure. All efforts will be made to make the subjects as comfortable as possible. A member of the study staff will explain the procedure thoroughly to the subject, allowing for maximal understanding and comfort. The testing can be stopped at any time at the subjects' request. A qualified physician/nurse will be on site or reachable by pager during all study visits in the unlikely event that an adverse event occurs.

The likelihood for the need for medical or professional intervention for a participant in this study is reduced by the protocol enrollment criteria that specify that we will enroll only medically stable, healthy adults to the study. Subjects will be asked to report adverse events at any time by calling study staff and will be asked to report adverse events at each study visit.

Risks of blood draws

Risks: The discomfort associated with removing (by catheter from a vein) is a slight pinch or pin prick when the sterile needle enters the skin. The risks include mild discomfort and/or a black and blue mark at the site of puncture. Less common risks include a small blood clot, infection or bleeding at the puncture site, and on rare occasions fainting during the procedure. There will be only a small amount of blood drawn (about 1 mL) each time.

Minimization: Blood draws will be taken by trained nursing staff at the Translational and Clinical Research Center or Center for Addiction Medicine at Massachusetts General Hospital. The total amount of blood drawn will not exceed 5 ccs per draw or 45 ccs per study day. If there are any concerns about a subject in need of clinical attention, the PI will be made aware of the issue immediately and will consult with appropriate medical personnel to determine appropriate steps.

Potential Benefits

There is no direct benefit to participating in this research. Some participants may find that talking about marijuana use increases their awareness of any issues related to drug use. Any participant who asks about treatment will be provided information regarding local drug treatment programs.

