Information developed from this study may help researchers in the future. Specifically it is expected that this study will provide valuable information to the field of acute marijuana effects on the brain.

MONITORING AND QUALITY ASSURANCE

All participants will have contact information for the principal investigator and the study coordinator if they have questions at any time. [name] is responsible for the overall management of the study and will maintain regular communication with all of the study staff. The PI will meet weekly with all study investigators to review the details of data acquisition and analysis as well as any minor problems. In the event of any minor or significant adverse event the PI will be contacted immediately. The PI is responsible for the generation of summary reports to the Partners HRC and to NIH, documenting this process and outcome.

Serious adverse events are not expected as a result of the study procedures. Should one occur, it will be reported by telephone or email by the principal investigator to the Partners IRB according to current PHRC Adverse Event Reporting Policy (version dated: March 13, 2007). All adverse events (if not serious) will be reported in writing to the Partner's Human Research Committee. All information regarding experimental subjects will be kept in the offices of the Principal Investigator. All data will be identified by a unique code number.

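### No staff-initiated adverse event enquiry is described after discharge from the last dosing visit or after voluntary withdrawal; from then on reporting depends on the participant calling in

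*Protocol*

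**What the plan says.** The collection rule is one sentence in the protocol, under Risks and Discomforts, fNIRS Risks, Minimization. It gives two routes:

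- Started by the participant: "Subjects will be asked to report adverse events at any time by calling study staff".
- Started by staff, in the second half of the same sentence: "by calling study staff and will be asked to report adverse events at each study visit".

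Monitoring and Quality Assurance supports the first route ("All participants will have contact information for the principal investigator and the study coordinator if they have questions at any time") and covers what happens once an event is known ("In the event of any minor or significant adverse event the PI will be contacted immediately"). It does not add a further occasion on which staff ask.

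Section VIII (Participant Withdrawal) says that "participants may stop being in the study at any time or decide not to join the study". It describes no exit contact, no adverse event question on leaving and no record of the reason.

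The section on dronabinol risks says: "Duration of action for psychoactive effects is 4 to 6 hours". Section X places the third fNIRS session before discharge, at about 220 min after dosing in Phase 2A and about 280 min in Phase 2B.

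The SAP contains no adverse event analysis.

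**The concern.** Once a participant goes home, staff ask about later events only if there is another visit. After the final dosing visit of a phase, or after a participant chooses not to return, no such visit is scheduled, and an event is recorded only if the participant calls.

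What is at stake is how complete the safety record is for single doses of up to 80 mg, with or without ethanol. The protocol describes dronabinol's effects as dose-related and mentions orthostatic hypotension and syncope. Events that begin or persist after release are therefore worth asking about, and they lie outside what in-visit monitoring can see. A second, smaller loss is the reason for leaving. The SAP (Missing Data) keeps only visits with both scans and relies on the multi-level model for the rest. A recorded reason would help in judging whether lost visits relate to treatment.

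**Working it through.** The documents give no adverse event rate, count or power figure, so there is no stated figure to reproduce. Two checks are possible.

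**1. Share of dosing visits with no later scheduled visit in the same phase**

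For a completer with v dosing visits, only the last has no later visit, so the share is 1/v. Maximum enrolment and dosing visits come from protocol Sections V and X. The number of active dronabinol visits per completer follows from each design. Expected active last visits = N × active visits ÷ v, which assumes that active dosing is balanced over visit positions in 2A and 2B.

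| Phase | N | v | Share last (1/v) | Dosing visits (N × v) | Last visits | Active visits | Expected active and last |
|---|---|---|---|---|---|---|---|
| 1 | 100 | 1 | 100% | 100 | 100 | 100 × 1 = 100 | 100 |
| 2A | 200 | 2 | 50% | 400 | 200 | 200 × 1 = 200 | 200/2 = 100 |
| 2B | 200 | 4 | 25% | 800 | 200 | 200 × 2 = 400 | 400/4 = 100 |
| 3 | 60 | 3 | 33% | 180 | 60 | 60 × 3 = 180 | 180/3 = 60 |
| Total | | | | 1,480 | 560 | 880 | 360 |

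At full enrolment with everyone completing, 560/1,480 = 38% of dosing visits and 360/880 = 41% of active dronabinol visits have passive reporting alone after discharge. The SAP gives 150 participants for 2A and 2B together. On that number the share of dosing visits runs from 150/600 = 25% (all in 2B) to 150/300 = 50% (all in 2A). Section X allows re-enrolment in a later phase, and each participant who returns lowers these shares.

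**2. Last scheduled scan against the stated duration of effect (240 to 360 min)**

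- Phase 2A, about 220 min: 240 − 220 = 20 min and 360 − 220 = 140 min, so the scan falls 20 to 140 min before the stated end of psychoactive effects.
- Phase 2B, about 280 min: 280 − 240 = 40 min after the lower end and 360 − 280 = 80 min before the upper end. The last 2B blood sample, at 300 min, is 60 min before the upper end.

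The interval from dosing to discharge is not stated. The roughly 7-hour visit length in Section V does not fix it, because pre-dose procedures take part of that time. The 2B requirement to stay is tied to breath alcohol alone. Part of the effect period may therefore fall after release; the documents do not show that it does.

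**The case against.** The strongest reply is that the period after discharge is covered. Participants are explicitly asked to call at any time, all of them hold contact details, and the principal investigator is told at once of any event. After dosing in 2A and 2B, heart rate, blood pressure and the drug-effect questionnaires are taken every 20 minutes. The protocol puts peak effect at 2 to 4 hours, so much of it falls inside the visit. In 2B, participants also stay until breath alcohol is below 0.01. The aims and both primary outcomes concern brain activity and performance, not tolerability. The visit schematics and consent pages are not available, so a closing contact described only there cannot be excluded. The SAP, dated 2022, speaks of scan collection in the past tense, so a prospective change may come too late.

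Most of this stands and limits the point. It does not remove it: a request to call is passive, and no visible text has staff ask after the last discharge.

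A reader might go further in four ways that the documents do not support:

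- **That terminated participants are also lost.** The stated rule, "Subjects will be terminated from the study if BrAC > 0" or on signs of intoxication, applies on arrival at a 2B visit, before dosing. That person is at a visit where earlier doses can be asked about.
- **That 50% or 25% of events go unrecorded.** These are shares of exposures. Only events after discharge that nobody calls in could be missed, and the documents allow no estimate of how many.
- **That events causing withdrawal are the most likely to be missed.** No text or figure supports this. An event that stops someone during a visit is seen by staff, and a troubling event at home could equally prompt a call.
- **That event rates in the more intoxicating conditions are biased downward.** The SAP plans no adverse event comparison, and the direction and size of any bias cannot be derived.

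**Conclusion.** The point holds as a modest gap in ascertainment. On the visible text, staff-initiated enquiry stops at the last dosing visit and at voluntary withdrawal. For completers, passive reporting alone follows 1 of 2 dosing visits in 2A, 1 of 4 in 2B, 1 of 3 in Phase 3 and the only visit in Phase 1. These shares assume full completion and no return in a later phase; the counts of active visits also assume balanced order. The same gap follows the last dosing visit before any voluntary withdrawal.

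No planned result is threatened. This is a low-cost improvement to the safety record, and it is resolved if a closing contact was already made in practice and is documented.

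**What to change.** Amend the reporting sentence under fNIRS Risks, Minimization, so that staff ask about adverse events once, by text or phone, within a fixed short interval after every dosing visit. This includes the last visit and the last one before a voluntary withdrawal. Use the same wording and timing after active and placebo visits, and record any reason for leaving at that contact. The text-message channel already used for appointment reminders (Section VI) can carry the prompt for those who gave permission.

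If data collection is complete, report adverse events with the ascertainment limit stated: staff asked at study visits, and participants had to call in otherwise.

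The cost is a wording change, one brief contact per dosing visit, a little staff time and slightly higher reported event rates.
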